1.2.1.3 Clinical Data

Based on the positive preclinical results described above, the clinical development program of PM01183 was started in March 2009. Currently, this program comprises three phase I single-agent studies (two in solid tumors and one in acute adult leukemia patients), five phase Ib combination studies with gemcitabine, capecitabine, doxorubicin, cisplatin, or paclitaxel with or without bevacizumab, in patients with selected advanced solid tumors, and four phase II studies: one trial as single agent or in combination with gemcitabine as second-line therapy in advanced non-small cell lung cancer (NSCLC), and three studies as single agent in second-line pancreatic cancer, in BRCA-mutated or in BRCA-unselected metastatic breast cancer patients and in platinum-resistant/refractory ovarian cancer. As of 15 January 2014, 366 patients (331 with solid tumors and 35 with advanced acute leukemia) had been treated with PM01183 in clinical trials within the clinical development program of this compound: 198 patients in phase I trials (35 with advanced acute leukemia) and 168 patients in phase II trials.

The two phase I trials which were exploring single-agent PM01183 schedules in solid tumor patients finished recruitment and a recommended dose (RD) was selected for further study in phase II trials. The first-in-human study (FiM) (PM1183-A-001-08) explored PM01183 administered as a 1-hour i.v. infusion every three weeks (q3wk) in patients with solid tumors. The RD was established at 4.0 mg/m²/q3wk [48]; since PM01183 clearance was found to be unrelated to body surface area (BSA), all patients in the RD expansion cohort were treated at an equivalent flat dose (FD) of 7.0 mg q3wk. In this and subsequent studies, the median terminal plasma half-life was around 60 hours, though inter-individual variability was high. No evidence of drug accumulation was found. Non-hematological toxicity was generally mild and reversible. Standard antiemetic prophylaxis was used at the RD to control grade 2 nausea and/or vomiting. Hematological toxicity, particularly grade 4 non-febrile neutropenia, was the most relevant toxicity and occurred in 40% of patients at the RD in the single-agent phase I studies. Neutropenia was generally predictable and short-lasting, and rarely caused treatment delays. In the FiM study (Day 1, q3wk) nadir usually occurred during the

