second week. One of 15 patients treated at the RD had a dose-limiting toxicity (grade 4 thrombocytopenia). No cases of febrile neutropenia occurred in this study, although patient selection might have played a role.

To explore the feasibility of an alternative schedule (Day 1 and 8, q3wk), a second phase I trial (PM1183-A-005-11) was started in advanced non-colorectal cancer patients following a prospective FD escalation. The RD was 5 mg FD on Day 1 and 8 q3wk; myelosuppression limited further dose escalation (around 40% of patients developed grade 4 neutropenia). Severe neutropenia was reversible in all cases, but two patients at the RD had grade 4 neutropenia lasting for more than one week. No unexpected toxicities were found. The safety profile of this schedule seems similar to that of the Day 1 q3wk trial, although neutropenia appeared more prolonged and may require additional dose adjustment.

Based on the results from single-agent phase I clinical trials, the Day 1 q3wk schedule has a good compliance and is more convenient. Therefore, the Day 1 q3wk schedule was selected for further clinical trials.

Antitumor activity has been observed with PM01183 either as single agent or in combination with other cytotoxics. Objective responses have been observed in patients with the following solid tumors (other than platinum-resistant ovarian cancer): pancreatic cancer, breast cancer, NSCLC, small cell lung cancer (SCLC), and other tumor types (neuroendocrine tumors, endometrial adenocarcinomas, bladder cancer, and soft tissue sarcoma). Results of the phase II trial in patients with platinum refractory/resistant ovarian cancer are summarized in the study rationale (Section [1.3.1](#)).

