5.7 EVALUATIONS DURING TREATMENT

The following assessments will be done while the patient is on treatment ([Table 6](#)).

Table 6. Evaluations during treatment.

	ASSESSMENT	TIME
1. Clinical examination	♦ Complete physical examination, including weight and calculation of BSA.	Cycle 2 and beyond: Day 1 of each cycle (always prior to treatment infusion).*
	♦ Performance status (ECOG PS). ♦ Vital signs: heart rate, blood pressure and body temperature.	Day 1 of each cycle (always prior to treatment infusion).*
	♦ Concomitant therapies.	Throughout the “on treatment” period.**
2. Laboratory tests	♦ Hematology: differential WBC counts (including neutrophil, lymphocyte and monocyte counts), platelet count and hemoglobin. ♦ Biochemistry: Liver function test (ALT, AST, AP, GGT, total bilirubin; direct bilirubin only if total bilirubin is abnormally high); total proteins, albumin, creatinine, CPK, glucose, calculated CrCL (as per Cockcroft and Gault’s formula), and serum electrolytes (Na^+ , K^+ , Cl^-).	Cycle 1: Day 8.* Cycle 2: Day 1 (always prior to treatment infusion) and Day 8.* Cycle 3 and beyond: Day 1 of each cycle (always prior to treatment infusion). * Any patient presenting grade 4 treatment-related AEs should have any relevant tests re-assessed at least within 72 hours until recovery to at least grade 3.
3. Pregnancy test (if women of childbearing potential)	Assessment of β -hCG (urine or serum).	Repeat if applicable.
4. ECG	Cardiac rhythm will be identified in ECG intervals of at least 30 seconds of duration, PR interval, QT interval (raw), heart rate and QRS complex.	Repeat if clinically indicated.
5. LVEF	ECHO or MUGA.	Repeat if clinically indicated. In patients treated with PLD (Arm B), to be repeated every four cycles (or more frequently, if clinically indicated). After exceeding a cumulative anthracycline dose of 450 mg/m^2 , LVEF will be assessed before each PLD infusion.
6. Pharmacokinetics (in the PM01183 treatment arm only)	-	A total of eight blood samples (before PM01183 treatment start, 5 min before the end of PM01183 infusion, and 1 hour and 168 hours after the end of PM01183 infusion) will be collected for pharmacokinetic PM01183 analyses in Cycle 1 (four samples) and in a second cycle (between Cycle 2 and 4) (four samples) in patients treated in Arm A. The second cycle with blood sample collection for PK will be assigned once the patient is randomized into Arm A (see details in Section 7.7.1).

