7. Pharmacogenetics	Only in those patients that give their written informed consent for the pharmacogenetic sub-study	One blood sample will be collected before treatment start in patients treated in Arm A along with the first pharmacokinetic sample of Cycle 1 for the pharmacogenetic sub-study.
8. Radiological tumor assessment	Contrast enhanced helical CT-scan or MRI, as clinically relevant.	Every eight weeks from randomization until evidence of PD.*

	ASSESSMENT	TIME
9. Tumor marker evaluation	CA-125.	Every eight weeks from randomization until evidence of PD, but only if baseline levels were higher than normal.*
10. Patient-reported outcomes	EORTC QLQ-C30 and EORTC QLQ-OV28 questionnaires.	Every eight weeks from randomization.*
11. Adverse events	As per NCI-CTCAE v.4.	Throughout the “on treatment” period.**

Regardless of the treatment administered, the same schedule of assessments will apply.

* A 3-day window will be allowed for laboratory tests and ECG, a 1-week window for tumor assessments as per RECIST v.1.1, tumor marker evaluation and patient-reported outcomes, and a 1-day window for clinical assessments (ECOG PS, vital signs, weight, BSA, etc.).

** “On treatment period” = from first infusion of the study treatment (PM01183, PLD or topotecan) to EOT [30 days after the day of the last dose administration, unless the patient starts a new antitumor therapy or dies (whichever occurs first), in which case the date of administration of this new therapy or the date of death will be considered the date of end of treatment].

AE, adverse event; ALT, alanine aminotransferase; AP, alkaline phosphatase; AST, aspartate aminotransferase; β -hCG, beta subunit of human chorionic gonadotropin; BSA, body surface area; CPK, creatine phosphokinase; CrCL, creatinine clearance; CT, computed tomography; ECG, electrocardiogram; ECHO, echocardiography; ECOG, Eastern Cooperative Oncology Group; EOT, end of treatment; EORTC, European Organization for Research and Treatment of Cancer; GGT, gamma glutamyltransferase; LVEF, left ventricular ejection fraction; MRI, magnetic resonance imaging; MUGA, multiple-gated acquisition scan; NCI-CTCAE, National Cancer Institute Common Terminology Criteria for Adverse Events; PLD, pegylated liposomal doxorubicin; PS, performance status; RECIST, Response Evaluation Criteria in Solid Tumors, WBC, white blood cells.

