12.4 Clinical Laboratory Evaluation

12.4.1 Hematological Abnormalities

Hematological toxicities classified according to NCI-CTCAE v4 will be calculated for all cycles. The worst grade reached by each patient during treatment will also be calculated.

Table 12.4.1.1 Hematological abnormalities, worst grade per patient

Listing 12.4.1.2 Hematological tests not assessed at any treatment visit by patient

Treatment arm*	Patient id.	Lab. test
	...	
	...	

*PM01183, PLD or Topotecan

Table 12.4.1.3 Hematological abnormalities, worst grade per cycle

Table 12.4.1.4 Hematological abnormalities, worst grade per cycle by cycle

Listing 12.4.1.5 Hematological tests not assessed by patient and cycle

Treatment arm*	Patient id.	Cycle	Lab. test
	...		
	...		

*PM01183, PLD or Topotecan

Listing 12.4.1.6 Grade 3/4 hematological abnormalities. Worst grade by cycle

Treatment arm*	Patient id.	Cycle	Test	Grade

*PM01183, PLD or Topotecan

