** Total bilirubin, AP, GGT, CPK, creatinine, hyperglycemia, hypernatremia, hyperkalemia, hypoglycemia, hyponatremia, hypokalemia and hypoalbuminemia.

Median intercycle figures showing PM01183 and Control arms for laboratory values will be added.

- Figure 12.4.4.6 Median nadir values for platelets
- Figure 12.4.4.7 Median nadir values for neutrophils
- Figure 12.4.4.8 Median peak values for AST
- Figure 12.4.4.9 Median peak values for ALT

Example intercycle graph

[figure not shown]

Table 12.4.4.10 Fisher exact test. Worst grade <3 vs. grade ≥ 3 by patient

	PM01183		Control		p-value
	Grade <3	Grade ≥ 3	Grade <3	Grade ≥ 3	
Thrombocytopenia					
Neutropenia					
ALKP					
Bilirubin					
SGOT-AST					
SGPT-ALT					
CPK					
Nausea					
Vomiting					
Fatigue					
Other*					

*Any drug-related toxicity present in $\geq 5\%$ of patients in any group.

Table 12.4.4.11 Fisher exact test. Worst grade <4 vs. grade ≥ 4 by patient

	PM01183		Control		p-value
	Grade <4	Grade ≥ 4	Grade <4	Grade ≥ 4	
Thrombocytopenia					
Neutropenia					
ALKP					
Bilirubin					
SGOT-AST					
SGPT-ALT					
CPK					
Nausea					
Vomiting					
Fatigue					
Other*					

*Any drug-related toxicity present in $\geq 5\%$ of patients in any group.

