12.5 Subgroup Analyses Related to Safety

Information for laboratory abnormalities comes from hematology/biochemistry forms and not from AE form.

Table 12.5.1 Worst grade 3/4 by patient in special subgroups (Age)

Laboratory abnormalities/ drug-related AEs	<65 years-old			≥65 years-old		
	No. of patients evaluated	Grade 3/4	%	No. of patients evaluated	Grade 3/4	%
PM01183						
Thrombocytopenia						
Neutropenia						
ALKP						
Bilirubin						
SGOT-AST						
SGPT-ALT						
CPK						
Nausea						
Vomiting						
Fatigue						
Other*						
Control						
Thrombocytopenia						
Neutropenia						
ALKP						
Bilirubin						
SGOT-AST						
SGPT-ALT						
CPK						
Nausea						
Vomiting						
Fatigue						
Other*						

*Any drug-related toxicity present in >=5% of patients in any group.

Table 12.5.2 Worst grade 3/4 by cycle in special subgroups (Age)

Laboratory abnormalities/ drug-related AEs	<65 years-old			≥65 years-old		
	No. of cycles evaluated	Grade 3/4	%	No. of cycles evaluated	Grade 3/4	%
PM01183						
Thrombocytopenia						
Neutropenia						
ALKP						
Bilirubin						
SGOT-AST						
SGPT-ALT						
CPK						
Nausea						
Vomiting						
Fatigue						
Other*						
Control						
Thrombocytopenia						
Neutropenia						
ALKP						
Bilirubin						
SGOT-AST						
SGPT-ALT						
CPK						
Nausea						
Vomiting						
Fatigue						
Other*						

*Any drug-related toxicity present in $\geq 3\%$ of cycles in any group.

Table 12.5.3 Worst grade 3/4 by patient in special subgroups (Race)

Laboratory abnormalities/ drug-related AEs	White			Other		
	No. of patients evaluated	Grade 3/4	%	No. of patients evaluated	Grade 3/4	%
PM01183						
Thrombocytopenia						
Neutropenia						
ALKP						
Bilirubin						
SGOT-AST						
SGPT-ALT						
CPK						
Nausea						
Vomiting						
Fatigue						
Other*						
Control						
Thrombocytopenia						
Neutropenia						
ALKP						
Bilirubin						
SGOT-AST						
SGPT-ALT						
CPK						
Nausea						
Vomiting						
Fatigue						
Other*						

*Any drug-related toxicity present in $\geq 5\%$ of patients in any group.

Table 12.5.4 Worst grade 3/4 by cycle in special subgroups (Race)

Laboratory abnormalities/ drug-related AEs	White			Other		
	No. of cycles evaluated	Grade 3/4	%	No. of cycles evaluated	Grade 3/4	%
PM01183						
Thrombocytopenia						
Neutropenia						
ALKP						
Bilirubin						
SGOT-AST						
SGPT-ALT						
CPK						
Nausea						
Vomiting						
Fatigue						
Other*						
Control						
Thrombocytopenia						

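### From Cycle 3 no mid-cycle blood count is scheduled, so the SAP's by-cycle nadir figures and worst-grade tables will understate later neutropenia and thrombocytopenia

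*SAP*

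**What the plan says.** **Sampling.** Protocol 5.7 (Table 6) schedules laboratory tests on Day 8 of Cycle 1, then "Cycle 2: Day 1 (always prior to treatment infusion) and Day 8", and then "Cycle 3 and beyond: Day 1 of each cycle (always prior to treatment infusion"). The Schedule of Assessments agrees: further cycles have no Day 8 mark for laboratory tests. On timing, "A 3-day window will be allowed for laboratory tests and ECG".

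**Re-treatment.** Protocol 6.5 (Tables 8 to 10) requires a Day 1 neutrophil count of at least 1.5 × 10⁹/l for all three drugs. Platelets must be at least 100 × 10⁹/l for PM01183 and topotecan and at least 75 × 10⁹/l for PLD.

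**Nadir timing.** Protocol 1.2.1.3 says of PM01183: "In the FiM study (Day 1, q3wk) nadir usually occurred during the" second week. It also describes the neutropenia as generally short.

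**Outputs.** SAP 7.2 and 12.4.1 grade haematology over all cycles, including "Table 12.4.1.4 Hematological abnormalities, worst grade per cycle by cycle". SAP 12.4.4 adds intercycle figures by arm: nadir platelets (12.4.4.6), "Median nadir values for neutrophils" (12.4.4.7), and peak AST and ALT (12.4.4.8 and 12.4.4.9). SAP 12.5 repeats neutropenia and thrombocytopenia by cycle in Tables 12.5.2, 12.5.4, 12.5.6, 12.5.8, 12.5.10 and 12.5.12, with the source stated as: "Information for laboratory abnormalities comes from hematology/biochemistry forms and not from AE form". SAP 12.2.1 likewise prefers laboratory results to adverse event reports for these toxicities.

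The SAP does not define nadir. It does not say whether a Day 1 count belongs to the cycle it opens or the one it closes, and it has no rule for cycles without a post-dose count.

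**The concern.** A by-cycle display is where a reader looks for cumulative marrow toxicity. Here the sampling changes between Cycle 2 and Cycle 3, from a count in the second week to a count taken just before dosing. The later count is also selected, because the cycle is normally given only if the count has recovered. A rise in the plotted nadir, or a fall in the per-cycle grade 3/4 percentage, from Cycle 3 would be produced at least partly by the schedule.

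The planned data checks would not reveal this. Listing 12.4.1.5 shows tests not assessed by patient and cycle, but the scheduled Day 1 test will have been done. The missing-value rule in SAP 8.8 does not apply for the same reason, so the cycle counts as evaluated.

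Neutropenia was the most relevant PM01183 toxicity in phase I (Protocol 1.2.1.3), and myelosuppression shaped the choice of dose (Protocol 1.4). It is therefore a toxicity whose course over cycles readers will examine.

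**Working it through.** The plan gives no figure of its own to reproduce. The check sets the schedule against the outputs, derives a bound, and then sizes the detection gap under stated assumptions.

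**1. Scheduled counts**

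| Cycle | Scheduled counts | Taken after dosing in that cycle |
|---|---|---|
| 1 | Screening, Day 8 | 1 |
| 2 | Day 1 pre-dose, Day 8 | 1 |
| 3 onward | Day 1 pre-dose | 0 |

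**2. Bound from the re-treatment rule.** Take a dosed Cycle 3 or later whose only count is the Day 1 sample that qualified the patient. Its recorded neutrophil minimum is at least 1.5 × 10⁹/l. Its platelet minimum is at least 100 × 10⁹/l (75 for PLD). If more than half the patients at a plotted cycle have only that sample, more than half the values are at or above the threshold, and so is the median. The true nadir does not enter.

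**3. Chance that a scheduled sample falls inside a grade 4 episode.** Assumptions: the centre of the episode is uniform over the second week (day 8 to day 15, a span of 7 days), and the episode lasts *d* days. Neither is given in the protocol; the lengths reflect its description of short neutropenia, with 10 days as an extreme. A sample on day *s* is inside the episode if it lies within *d*/2 of the centre.

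- Day 8: probability = (*d*/2)/7. For *d* = 3, 5, 7 and 10 this is 1.5/7 = 21%, 2.5/7 = 36%, 3.5/7 = 50% and 5/7 = 71%. Spreading the sample over ±3 days gives about the same.
- The cycle's own Day 1: at least 7 days before any centre, and *d*/2 is at most 5, so 0%.
- The next cycle's Day 1 (day 22): at least 7 days after any centre, so 0%. If drawn up to 3 days early (days 19 to 22), it is still 0% for 3 to 7 days and about 2% for 10 days.

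**4. Illustration of the recorded rate.** The expected rate from a given source is the true per-cycle rate times the share of episodes that source finds. Protocol 1.4 reports grade 4 neutropenia in 9% of patients at or below 3.2 mg/m² and 47% above. These are per-patient figures, borrowed only as the ends of an assumed per-cycle range.

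- Cycles 1-2, Day 8 sample alone, 3- to 7-day episodes: 0.09 × 0.214 to 0.09 × 0.50 = 1.9% to 4.5%; 0.47 × 0.214 to 0.47 × 0.50 = 10.1% to 23.5%.
- Cycle 3 onward, unscheduled tests finding an assumed 0% to 25% of episodes: 0 to 0.09 × 0.25 = 0% to 2.2%; 0 to 0.47 × 0.25 = 0% to 11.7%.

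Even Cycles 1-2 miss many episodes, but the sampling there is the same in both cycles and all arms. Nadir timing is documented for PM01183 only; nothing is assumed for PLD or topotecan.

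**The case against.** Several points on the other side stand and limit the conclusion.

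- **Later events are not invisible.** A failed Day 1 count is itself a scheduled sample. It leads to reassessment within a week (Protocol 6.5), a detected grade 4 event to retesting within 72 hours (Table 6), and there are end-of-treatment laboratory tests (Protocol 5.8). A reader might infer that later cycles will look free of myelosuppression. The documents support only understatement.
- **Some decline would be genuine.** Protocol 6.6 provides for secondary CSF prophylaxis after grade 4 or febrile neutropenia and dose reduction on recurrence.
- **The main comparisons are per patient.** Fisher Tables 12.4.4.10 and 12.4.4.11 and shift Table 12.4.4.2 include the Day 8 counts of Cycles 1-2. The interim safety analysis tests febrile neutropenia, every episode of which must be reported within 24 hours. A reader might infer that these are compromised; the documents do not support that.
- **Other by-cycle outputs exist:** delays (12.1.2.2.1), reductions (12.1.3.3) and adverse events (12.2.2.3 and 12.2.2.5). They help, but they also depend on detection. Protocol 7.4.1 admits laboratory abnormalities to the adverse event form only under set conditions, and SAP 12.2.1 concedes under-reporting.
- **Anaemia and AST/ALT differ.** Later Day 1 haemoglobin is informative. No passage places AST/ALT peaks mid-cycle, and PLD has no AST/ALT re-treatment threshold.
- **Cycle length.** A reader might object to comparing 21-day with 28-day cycles in Table 12.5.10. With one dosing course per cycle, percentage of cycles is a legitimate unit, and a patient-week rate would still count unobserved weeks.

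The example intercycle graph was not visible. That the figures cover all cycles is inferred from their description and from SAP 12.4.1.

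**Conclusion.** The concern holds for the by-cycle neutrophil and platelet outputs. From Cycle 3 no scheduled in-cycle sample is taken near the documented PM01183 nadir, and the one that is taken normally has to have recovered. The bound of 1.5 × 10⁹/l needs no assumption beyond the qualifying Day 1 sample being the cycle's only count. The contrast of 21% to 50% with 0% rests on the assumed nadir timing and episode length. The illustrated rates also depend on the assumed true rate and the yield of unscheduled tests.

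The overall size across all cycles cannot be fixed from the documents. A reader might use the planning PFS medians as time on treatment to obtain the share of cycles affected in each arm. The documents do not support that, because treatment also stops for toxicity, refusal or the need for more than two dose reductions (Protocol 5.2.1.2). The issue is a correctable fault in presentation and denominators; it does not undermine the per-patient safety comparison.

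**What to change.** In the SAP:

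1. Restrict Figures 12.4.4.6 and 12.4.4.7 to Cycles 1-2, where every arm has a scheduled Day 8 count. Do the same for the neutropenia, leukopenia and thrombocytopenia rows, where present, of the by-cycle tables used for comparison (12.4.1.3, 12.4.1.4, and 12.5.2, 12.5.4, 12.5.6, 12.5.8, 12.5.10 and 12.5.12).
2. If later cycles are shown, present them separately as *lowest recorded value*. State which cycle a Day 1 count is assigned to, and print the number of cycles with a mid-cycle count that is not a pre-dose sample.
3. Footnote that Day 8 sampling stops after Cycle 2 and that later mid-cycle counts are event-driven, so no trend across cycles is inferred. Do not use the later cycles with a mid-cycle count as the denominator for a rate: they are a selected set and would overstate it.
4. Keep anaemia and biochemistry for all cycles, and relabel the AST and ALT peak as *highest recorded value*.

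The cost is SAP wording and programming, with no extra samples and no change to patient management. The small downside is that the by-cycle myelosuppression comparison rests on fewer cycles.

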12.5 Subgroup Analyses Related to Safety

Information for laboratory abnormalities comes from hematology/biochemistry forms and not from AE form.

Table 12.5.1 Worst grade 3/4 by patient in special subgroups (Age)

Laboratory abnormalities/ drug-related AEs	<65 years-old			≥65 years-old		
	No. of patients evaluated	Grade 3/4	%	No. of patients evaluated	Grade 3/4	%
PM01183						
Thrombocytopenia						
Neutropenia						
ALKP						
Bilirubin						
SGOT-AST						
SGPT-ALT						
CPK						
Nausea						
Vomiting						
Fatigue						
Other*						
Control						
Thrombocytopenia						
Neutropenia						
ALKP						
Bilirubin						
SGOT-AST						
SGPT-ALT						
CPK						
Nausea						
Vomiting						
Fatigue						
Other*						

*Any drug-related toxicity present in >=5% of patients in any group.

Table 12.5.2 Worst grade 3/4 by cycle in special subgroups (Age)

Laboratory abnormalities/ drug-related AEs	<65 years-old			≥65 years-old		
	No. of cycles evaluated	Grade 3/4	%	No. of cycles evaluated	Grade 3/4	%
PM01183						
Thrombocytopenia						
Neutropenia						
ALKP						
Bilirubin						
SGOT-AST						
SGPT-ALT						
CPK						
Nausea						
Vomiting						
Fatigue						
Other*						
Control						
Thrombocytopenia						
Neutropenia						
ALKP						
Bilirubin						
SGOT-AST						
SGPT-ALT						
CPK						
Nausea						
Vomiting						
Fatigue						
Other*						

*Any drug-related toxicity present in $\geq 3\%$ of cycles in any group.

Table 12.5.3 Worst grade 3/4 by patient in special subgroups (Race)

Laboratory abnormalities/ drug-related AEs	White			Other		
	No. of patients evaluated	Grade 3/4	%	No. of patients evaluated	Grade 3/4	%
PM01183						
Thrombocytopenia						
Neutropenia						
ALKP						
Bilirubin						
SGOT-AST						
SGPT-ALT						
CPK						
Nausea						
Vomiting						
Fatigue						
Other*						
Control						
Thrombocytopenia						
Neutropenia						
ALKP						
Bilirubin						
SGOT-AST						
SGPT-ALT						
CPK						
Nausea						
Vomiting						
Fatigue						
Other*						

*Any drug-related toxicity present in $\geq 5\%$ of patients in any group.

Table 12.5.4 Worst grade 3/4 by cycle in special subgroups (Race)

Laboratory abnormalities/ drug-related AEs	White			Other		
	No. of cycles evaluated	Grade 3/4	%	No. of cycles evaluated	Grade 3/4	%
PM01183						
Thrombocytopenia						
Neutropenia						
ALKP						
Bilirubin						
SGOT-AST						
SGPT-ALT						
CPK						
Nausea						
Vomiting						
Fatigue						
Other*						
Control						
Thrombocytopenia						
Neutropenia						
ALKP						
Bilirubin						
SGOT-AST						
SGPT-ALT						
CPK						
Nausea						
Vomiting						
Fatigue						
Other*						

*Any drug-related toxicity present in $\geq 3\%$ of cycles in any group.

Table 12.5.5 Worst grade 3/4 by patient in special subgroups (Number of prior chemotherapy lines)

Laboratory abnormalities/ drug-related AEs	1-2			3		
	No. of cycles evaluated	Grade 3/4	%	No. of cycles evaluated	Grade 3/4	%
PM01183						
Thrombocytopenia						
Neutropenia						
ALKP						
Bilirubin						
SGOT-AST						
SGPT-ALT						
CPK						
Nausea						
Vomiting						
Fatigue						
Other*						
Control						
Thrombocytopenia						
Neutropenia						
ALKP						
Bilirubin						
SGOT-AST						
SGPT-ALT						
CPK						
Nausea						
Vomiting						
Fatigue						
Other*						

*Any drug-related toxicity present in $\geq 5\%$ of patients in any group.

Table 12.5.6 Worst grade 3/4 by cycle in special subgroups (Number of prior chemotherapy lines)

Laboratory abnormalities/ drug-related AEs	1-2			3		
	No. of cycles evaluated	Grade 3/4	%	No. of cycles evaluated	Grade 3/4	%
PM01183						
Thrombocytopenia						
Neutropenia						
ALKP						
Bilirubin						
SGOT-AST						
SGPT-ALT						
CPK						
Nausea						
Vomiting						
Fatigue						
Other*						
Control						
Thrombocytopenia						
Neutropenia						
ALKP						
Bilirubin						
SGOT-AST						
SGPT-ALT						
CPK						
Nausea						
Vomiting						
Fatigue						
Other*						

*Any drug-related toxicity present in $\geq 3\%$ of cycles in any group.

Table 12.5.7 Worst grade 3/4 by patient in special subgroups (Geographical area)

Laboratory abnormalities/ drug-related AEs	USA			Europe			Rest of the world		
	No. of patients evaluated	Grade 3/4	%	No. of patients evaluated	Grade 3/4	%	No. of patients evaluated	Grade 3/4	%
PM01183									
Thrombocytopenia									
Neutropenia									
ALKP									
Bilirubin									
SGOT-AST									
SGPT-ALT									
CPK									
Nausea									
Vomiting									
Fatigue									
Other*									
Control									
Thrombocytopenia									
Neutropenia									
ALKP									
Bilirubin									
SGOT-AST									
SGPT-ALT									
CPK									
Nausea									
Vomiting									
Fatigue									
Other*									

*Any drug-related toxicity present in $\geq 5\%$ of patients in any group.

Table 12.5.8 Worst grade 3/4 by cycle in special subgroups (Geographical area)

Laboratory abnormalities/ drug-related AEs	USA			Europe			Rest of the world		
	No. of patients evaluated	Grade 3/4	%	No. of patients evaluated	Grade 3/4	%	No. of patients evaluated	Grade 3/4	%
PM01183									
Thrombocytopenia									
Neutropenia									
ALKP									
Bilirubin									
SGOT-AST									
SGPT-ALT									
CPK									
Nausea									
Vomiting									
Fatigue									
Other*									
Control									
Thrombocytopenia									
Neutropenia									
ALKP									
Bilirubin									
SGOT-AST									
SGPT-ALT									
CPK									
Nausea									
Vomiting									
Fatigue									
Other*									

*Any drug-related toxicity present in $\geq 3\%$ of cycles in any group.

Table 12.5.9 Worst grade by patient comparison vs. PLD

Laboratory abnormalities/ drug-related AEs	Grade																			
	PM01183										PLD									
	0		1		...		G≥1		G≥3		0		1		...		G≥1		G≥3	
	N	%	N	%	N	%	N	%	N	%	N	%	N	%	N	%	N	%	N	%
Thrombocytopenia																				
Neutropenia																				
ALKP																				
Bilirubin																				
SGOT-AST																				
SGPT-ALT																				
CPK																				
Nausea																				
Vomiting																				
Fatigue																				
Other*																				

*Any drug-related toxicity present in >=5% of patients in any group.

Table 12.5.10 Worst grade by cycle comparison vs. PLD

Laboratory abnormalities/ drug-related AEs	Grade																			
	PM01183										PLD									
	0		1		...		G≥1		G≥3		0		1		...		G≥1		G≥3	
	N	%	N	%	N	%	N	%	N	%	N	%	N	%	N	%	N	%	N	%
Thrombocytopenia																				
Neutropenia																				
ALKP																				
Bilirubin																				
SGOT-AST																				
SGPT-ALT																				
CPK																				
Nausea																				
Vomiting																				
Fatigue																				
Other*																				

*Any drug-related toxicity present in >=5% of patients in any group.

Table 12.5.11 Worst grade by patient comparison vs. topotecan

Laboratory abnormalities/ drug-related AEs	Grade																			
	PM01183										Topotecan									
	0		1		...		G≥1		G≥3		0		1		...		G≥1		G≥3	
	N	%	N	%	N	%	N	%	N	%	N	%	N	%	N	%	N	%	N	%
Thrombocytopenia																				
Neutropenia																				
ALKP																				
Bilirubin																				
SGOT-AST																				
SGPT-ALT																				
CPK																				
Nausea																				
Vomiting																				
Fatigue																				
Other*																				

*Any drug-related toxicity present in >=5% of patients in any group.

Table 12.5.12 Worst grade by cycle comparison vs. topotecan

Laboratory abnormalities/ drug-related AEs	Grade																			
	PM01183										Topotecan									
	0		1		...		G≥1		G≥3		0		1		...		G≥1		G≥3	
	N	%	N	%	N	%	N	%	N	%	N	%	N	%	N	%	N	%	N	%
Thrombocytopenia																				
Neutropenia																				
ALKP																				
Bilirubin																				
SGOT-AST																				
SGPT-ALT																				
CPK																				
Nausea																				
Vomiting																				
Fatigue																				
Other*																				

*Any drug-related toxicity present in >=5% of patients in any group.

